Pen Bay Medical Center
MaineHealth

Official Title: ATIVO Study – Anticoagulation Therapy In The Very Old

NCT #: 03103763

Protocol Version 2.1, dated 13 DEC 2018

**ATIVO STUDY
ANTICOAGULATION THERAPY IN THE VERY OLD**

Principal Investigators: *[name]*
[name]
Penobscot Bay Medical Center
Anticoagulation Service

List of Abbreviations

ACS – Penobscot Bay Medical Center Anticoagulation Services

PBMC – Penobscot Bay Medical Center

TTR – Time in Therapeutic Range

1 Introduction:

Atrial fibrillation increases the risk of stroke by allowing the formation of clot within the left atrium and left atrial appendage. This clot is then able to embolise to the cerebral circulation producing vascular occlusion and stroke often with severe disabling deficit or death. Anticoagulation has been shown to substantially decrease the risk of stroke in patients with atrial fibrillation. Unfortunately anticoagulation increases the risk of major hemorrhage. Almost 15% of patients with atrial fibrillation followed by the Pen Bay Anticoagulation Service are over 90 years old. There is presently no clear guidance for anticoagulation in the very old. Our preliminary data suggest that in this very old group there is an increased risk of both thrombotic and hemorrhagic complications but that stroke prevention can be safely achieved.

2 Study Objectives

This study is designed to evaluate the efficacy and safety of warfarin anticoagulation in the very old and attempt to identify risk factors which may impede safe and effective anticoagulation.

3 Study Design

This is a prospective registry study with data being collected continuously for 24 months.

4 Subject Selection and Withdrawal

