4.4 Early Withdrawal of Subjects

Subjects may withdraw from study participation at any time without any effect on their care at the ACS. Additionally, subjects will be withdrawn early from the study if the investigators are unable to communicate with them or obtain medical records.

5 Study Procedures

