5.2 Follow Up

Every 6 months (+/- 4 weeks), subjects will be contacted and follow up information will be obtained. When possible, these visits will be conducted when the subject has an appointment at the ACS and will be done in person. If the subject is no longer being seen by the ACS, information will be obtained by phone or by searching the subject's medical record. If needed, family or friends as designated by the subject at study enrollment, will be contacted in order to obtain information about the subject outcomes.

If the subject was enrolled utilizing an LAR, the study will be re-explained and assent will be obtained and documented in the source document prior to any study procedures.

Follow up Mini-Cog™ evaluations will only be done if the visit is done in person. See attached Follow-Up Data Collection Form for details regarding what information will be obtained at these visits.

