Official Title: **ATIVO Study – Anticoagulation Therapy in the Very Old**

NCT #: **03103763**

Statistical analysis plan

For the purpose of this study, we attempted to detect differences in outcomes among age groups (70-79, 80-89, and 90+) undergoing anticoagulation therapy at study enrollment and in 6-month intervals for 24 months. Descriptive statistics were used to summarize the demographic (age group, sex, and living arrangement) and clinical characteristics (mobility, alcohol use, CHADS2-VASc, Fragility score, mini Cog, and mobility scale) of patients included in the study, with continuous variables presented as a mean +- standard deviation and categorical variables as frequencies/percentages of the total. The primary outcome of interest was time in therapeutic range (TTR), a percentage of time that a patient's International Normalized Ratio (INR) values were in range over a 6-month period. Secondary outcomes were all-cause mortality, stroke, and major bleeding events. Student t tests and chi-squared tests were conducted to compare data between groups. Statistical significance was set at $P < .05$ with a 95% confidence interval.

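### Death, stroke and major bleeding appear to be compared as simple proportions although follow-up can end early; unequal withdrawal would bias this, in a direction set by a denominator the SAP does not state

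*SAP*

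**What the plan says.** The SAP is a single paragraph. On the outcomes: "Secondary outcomes were all-cause mortality, stroke, and major bleeding events". On method: "Student t tests and chi-squared tests were conducted to compare data between groups". It describes the age groups (70-79, 80-89, 90+) as compared "at study enrollment and in 6-month intervals for 24 months". It reports categorical characteristics as percentages, but gives no denominator for events.

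Protocol section 6 lists items to compare across the age decades and names no method. Section 5.3 puts the final visit at 24 months. Section 4.4 allows withdrawal at any time and adds that "subjects will be withdrawn early from the study if the investigators are unable to communicate with them or obtain medical records". Section 5.2 limits the loss. For subjects no longer seen by the anticoagulation service, "information will be obtained by phone or by searching the subject's medical record". The same section provides a further source where those two fall short, namely people close to the subject: "family or friends as designated by the subject at study enrollment, will be contacted in order to obtain information about the subject outcomes".

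Neither document mentions person-time, censoring, competing events or an expected withdrawal rate.

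**The concern.** For a yes/no event, the chi-squared test is the one of the two named tests that applies, and it compares proportions. A proportion over 24 months equals the 24-month risk only if everyone is observed until the event, death or month 24. Section 4.4 means that some subjects will not be. If the share lost differs between age groups, part of any difference in the table, or part of a missing difference, reflects follow-up and not risk.

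This bears on the study's purpose: "This study is designed to evaluate the efficacy and safety of warfarin anticoagulation in the very old". The Introduction says of preliminary data that "in this very old group there is an increased risk of both thrombotic and hemorrhagic complications". A reader of the final table needs to know whether a percentage is a 24-month risk, a risk among those fully followed, or a risk per interval. The SAP does not say.

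Death raises a separate question. It also shortens time at risk for stroke and bleeding, and it will presumably be more frequent at 90+. With no withdrawal, however, the proportion with a bleed is a correct risk of bleeding before death. It differs from the rate while alive, but it is not biased.

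**Working it through.** The documents give no sample size, event rate or withdrawal rate, so there is no figure of the plan to reproduce. The check is an illustration, and every rate in it is an assumption.

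**Inputs** (per 100 patient-years, 70-79 vs 90+): first major bleed 6 in both; death 4 vs 20; withdrawal 3 vs 8. Hazards are constant, withdrawal is independent of the event, and nothing is ascertained after withdrawal. T = 2 years (protocol section 5.3).

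**Bleeding.** With h = hb + hd + hw and F = 1 − exp(−hT):
- all enrolled as denominator: P = (hb/h) × F
- withdrawn without a bleed: W = (hw/h) × F
- event-free withdrawals dropped: P/(1 − W)

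At 90+, h = 0.34 and F = 0.4934, so P = 0.0871, W = 0.1161 and P/(1 − W) = 0.0871/0.8839 = 0.0985. At 70-79, h = 0.13 and F = 0.2289, so P = 0.1057, W = 0.0528 and P/(1 − W) = 0.1057/0.9472 = 0.1116. Without withdrawal (hw = 0) the risks are 0.1088 and 0.0936.

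**All-cause death**, vital status unknown after withdrawal: the same formulas with hd as the event and h = hd + hw. At 90+, h = 0.28 and F = 0.4288, so P = 0.3063, W = 0.1225 and P/(1 − W) = 0.3490. At 70-79, h = 0.07 and F = 0.1306, so P = 0.0747, W = 0.0560 and P/(1 − W) = 0.0791. Without withdrawal, 1 − exp(−2hd) = 0.0769 and 0.3297.

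| 24 months | No withdrawal | All enrolled | Withdrawals dropped |
|---|---|---|---|
| Bleeding, 70-79 | 10.9% | 10.6% | 11.2% |
| Bleeding, 90+ | 9.4% | 8.7% | 9.9% |
| Bleeding RR | 0.86 | 0.82 | 0.88 |
| Death, 70-79 | 7.7% | 7.5% | 7.9% |
| Death, 90+ | 33.0% | 30.6% | 34.9% |
| Death RR | 4.29 | 4.10 | 4.41 |

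Relative to no withdrawal, each risk ratio moves about 4% down or 3% up (bleeding 0.824/0.860 and 0.883/0.860; death 4.10/4.29 and 4.41/4.29).

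**Range.** With withdrawal at 90+ of 5, 8 or 15 per 100 patient-years (70-79 kept at 3), the bleeding RR is 0.85, 0.82 or 0.77 over all enrolled, and 0.87, 0.88 or 0.92 with withdrawals dropped. With withdrawal of 3 in both groups it is 0.86 either way, as without withdrawal.

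**Without competing death.** For one event with a true 24-month risk of 20% and 20% withdrawal, the proportion is 18.0% over all enrolled and 22.0% with withdrawals dropped. The sign reverses in the same way.

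**Per 6-month interval**, among those still followed at its start (T = 0.5): bleeding is 2.90% vs 2.76%, RR 0.95, against 0.96 without withdrawal. Withdrawal then moves the ratio by about 1%.

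**Sampling error.** With 100 per group (an assumption), the SE of the 24-month bleeding difference is √(0.1057 × 0.8943/100 + 0.0871 × 0.9129/100) = 0.042, or 4.2 points. Withdrawal moves the 90+ bleeding risk by about 0.65 points down or 0.5 up.

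**Person-time from visit data alone.** Let q = 1 − exp(−0.5h) and count half an interval for those who leave, die or have the event. The rate is (hb/h) × q/(0.5 − 0.25q). With q = 0.0629 and 0.1563 this gives 6.00 and 5.99 per 100 patient-years against a true 6.

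**The case against.** Much of the opposing case stands. No withdrawal rate appears anywhere, so unequal withdrawal is an assumption; with equal withdrawal the bleeding risk ratio barely moves. Section 5.2 keeps collecting outcomes by phone, records and designated contacts after a subject leaves the service, so the loss is confined to those who withdraw or cannot be traced. The SAP's reference to 6-month intervals may mean that events were tested per interval among those still followed, which would nearly remove the problem. The outcomes are secondary, and in a small registry sampling error may well exceed the bias.

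A reader might infer more: that the analysis understates the risk at 90+ and so makes the oldest group look safer than it is. The documents do not support that. It requires both more withdrawal at 90+ and all enrolled as the denominator, and neither is stated. The SAP's sentence on percentages concerns patient characteristics, and dropping event-free withdrawals reverses the sign.

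A reader might also calculate that, under the assumed rates, a bleeding hazard ratio of 1.23 at 90+ would appear as no difference in a 24-month table of all enrolled. Most of that (1.17) comes from death, which is a choice between risk and rate and not an error. Withdrawal accounts for about 1.228/1.173 = 1.05.

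The opposing case does not remove the gap itself. Unequal follow-up is possible under section 4.4, the named test makes no allowance for it, and no denominator is given that would let a reader judge the result.

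**Conclusion.** The concern holds in a limited form. The named tests imply a comparison of simple proportions, and that comparison is biased if withdrawal differs by age group. The direction cannot be determined from the documents. Under the assumed rates, the shift at 90+ is about half a percentage point for bleeding and about two points for death (30.6% or 34.9% against 33.0%). This rests on constant hazards, on withdrawal being more frequent at 90+, and on no ascertainment after withdrawal; the tracing in section 5.2 would make it smaller. That simple proportions were used is itself an inference from the list of tests. Severity is minor to moderate. A method that handles unequal follow-up directly is available at little cost.

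**What to change.** In the SAP, replace the chi-squared comparison for the three secondary event outcomes:

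- **All-cause death:** Kaplan-Meier curves with a log-rank test across the three age groups, censored at last contact.
- **Stroke and major bleeding:** 24-month cumulative incidence with death as a competing event, plus events per 100 patient-years with 95% confidence intervals, censored at last contact. Where exact dates are missing, count person-time by 6-month interval.
- **Reporting:** follow-up time, deaths and withdrawals by age group.

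The SAP is written in the past tense, so this may mean re-analysing collected data; the conduct of the study does not change. The cost is a little more analysis work and the extraction of event and last-contact dates. One assumption remains and should be stated: censoring treats withdrawal as unrelated to event risk within an age group.

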4.3 Subject Recruitment and Screening

Subjects will be recruited from the PBMC Anticoagulation Services (ACS) department. The medical records used by the ACS will be searched using age ≥ 70 and diagnosis of atrial fibrillation as search criteria. All patients aged 90 years or older who fit the criteria will be approached about participation in the study.

An equal number of patients from the ACS who are aged 80-89 years and, an equal number of patients from the ACS will be enrolled who are aged 70-79 years will be enrolled.

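### Student t tests pool the variance, and the decades are planned equal in size only at enrollment: at later visits the per-comparison error could move either side of 5%, which Welch's test avoids at almost no cost.

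*SAP*

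**What the plan says.** The SAP makes TTR over a 6-month period the primary outcome and compares three age groups (70-79, 80-89 and 90+) "at study enrollment and in 6-month intervals for 24 months". The method is one sentence: "Student t tests and chi-squared tests were conducted to compare data between groups". TTR is a percentage summarised on a continuous scale, so the t test is the one that applies to it. No unequal-variance version is mentioned. The threshold is given as follows: "Statistical significance was set at $P < .05$ with a 95% confidence interval".

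Protocol Section 4.3 has all eligible patients aged 90 or older approached, and for the younger decades "an equal number of patients from the ACS will be enrolled". Nothing is said about keeping the decades equal afterwards. Section 4.4 provides that "subjects will be withdrawn early from the study if the investigators are unable to communicate with them or obtain medical records". Section 5.2 foresees patients who are no longer seen by the anticoagulation service, and the SAP counts all-cause mortality as a secondary outcome.

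**The concern.** The pooled test estimates one common variance for both groups. With equal group sizes, unequal variances hardly affect its error rate. With unequal sizes they do: if the smaller group is the more variable, the standard error is too small and the test rejects too often; if it is the less variable, the test is conservative and loses power.

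Equal enrollment therefore protects the comparison at enrollment but not necessarily those at 6 to 24 months. If deaths and withdrawals fall more heavily on the 90+ group, later comparisons of 90+ with a younger decade are made with unequal numbers. Their validity then depends on the ratio of the TTR variances, which the plan does not discuss. Those comparisons concern the primary outcome in the age group the study was set up to examine.

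**Working it through.** **Inputs from the documents.** Threshold .05 per test, taken as two-sided because it is paired with a 95% confidence interval (sidedness is not stated). Student t test. Equal numbers per decade at enrollment.

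**Inputs assumed, because the documents give none.** Fifty patients enrolled per decade; 45 (90%) remaining at 70-79; 20 to 40 (40% to 80%) remaining at 90+; TTR SD 15 at 70-79 and 12, 15, 20 or 25 at 90+; normal data; and a direct two-group comparison of 90+ with 70-79.

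**Formula.** With sizes n1, n2 and SDs s1, s2, the variance of the difference in means is

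V_true = s1²/n1 + s2²/n2,

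whereas the pooled test in large samples uses

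V_pooled = s1²/n2 + s2²/n1.

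The actual two-sided error is 2[1 − Φ(1.96 × √(V_pooled/V_true))].

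**The plan's own figure.** If n1 = n2, or if s1 = s2, then V_pooled = V_true and the formula returns 5.0%, the stated threshold. Both inequalities are needed to move it.

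**Worked cases, 45 against 20 patients.**

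- 90+ SD 25: V_pooled = 225/20 + 625/45 = 25.14; V_true = 225/45 + 625/20 = 36.25; ratio 0.6935, square root 0.833; 1.96 × 0.833 = 1.632; error 10.3%.
- 90+ SD 20: V_pooled = 11.25 + 8.89 = 20.14; V_true = 5 + 20 = 25; ratio 0.8056, square root 0.898; 1.759; error 7.9%.
- 90+ SD 12: V_pooled = 11.25 + 3.20 = 14.45; V_true = 5 + 7.2 = 12.2; ratio 1.184, square root 1.088; 2.133; error 3.3%.

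**Student test, error (%) at nominal 5%, 45 patients at 70-79 with SD 15:**

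| Patients at 90+ | SD 12 | SD 15 | SD 20 | SD 25 |
|---|---|---|---|---|
| 40 | 4.7 | 5.0 | 5.4 | 5.7 |
| 32 | 4.2 | 5.0 | 6.2 | 7.0 |
| 25 | 3.7 | 5.0 | 7.1 | 8.7 |
| 20 | 3.3 | 5.0 | 7.9 | 10.3 |

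Simulation with normal data agrees to within about 0.1 percentage point (for example 10.4% in the last cell). In the same simulations Welch's test stays at about 5% in every cell.

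**Power.** With 45 against 20 patients, equal SDs of 15 and a true difference of 10 points, simulated power is 68.4% for Student and 67.4% for Welch. If the 90+ SD is 12, Student has about 75% and Welch about 80%.

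**The case against.** The strongest objection is that neither driver is in the documents. They give no group size, retention rate or SD of TTR, and nothing says that TTR varies more, or less, at 90+. Faster loss at 90+ is plausible, since the Protocol introduction reports more thrombotic and hemorrhagic complications in the very old, but no rate is given. Only unequal loss matters: if every decade shrinks in the same proportion, the error stays at 5%. Section 5.2 also limits loss, because patients who leave the service are followed by phone, medical record or designated contacts. With mild inputs the effect is small (5.4% for 40 patients and SD 20). All of this stands, and it is why the result is a range on both sides of 5%.

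A reader might infer that the plan carries a 6-10% error rate for its primary outcome. The documents do not support that. Those values need a smaller and also more variable 90+ group, and .05 is a threshold for each test. Multiplicity is a different and larger matter: three pairwise Student tests with equal sizes and equal SDs already give a family-wise error of about 12% at a single time point, and Welch leaves that unchanged.

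A reader might also infer a high risk of wrongly finding worse control in the very old. The errors above are two-sided and split evenly by direction. The rate in that direction is half: about 3.1% (32 patients, SD 20) to 5.2% (20 patients, SD 25), against 2.5% nominal.

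Finally, the SAP's wording does not settle whether equal variances were assumed when the tests were run. Read literally, it names the pooled test.

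**Conclusion.** The point holds as a conditional, minor one. The SAP names a test whose error rate is protected by equal group sizes, and equality is planned only at enrollment. Under the assumed values, one later comparison of 90+ with 70-79 could have an actual error anywhere from about 3% to about 10%, and exactly 5% if the variances are equal. The documents do not show where in that range the study lies, or on which side of 5%.

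The comparison at enrollment is unaffected if the planned equal numbers are achieved. Loss from the 90+ group does not touch the comparison of 70-79 with 80-89. The case for change does not depend on guessing the direction: Welch's test keeps about 5% whichever group is the more variable.

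**What to change.** In the SAP, replace Student t tests by Welch's t test for two-group comparisons of TTR and other continuous measures, and use Welch's ANOVA where the three decades are compared together. If Welch's version was in fact used, say so. Report the number of patients and the SD of TTR by decade at each visit, so that a reader can see whether the choice mattered.

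No new data are needed. Because the SAP is written in the past tense, the change probably means re-running the comparisons on existing data as well as editing the sentence. The price in power is about 1 percentage point at most in the setting shown, if the variances are equal. Multiplicity across decades and visits needs its own provision.

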5.4 Assessments

Mini-Cog™ (used by permission) is a validated screening tool used to detect dementia.⁵

CHA₂DS₂-VASc score is a validated tool for stroke risk stratification.³

HAS-BLED score is a validated schema for risk stratification for bleeding events among anticoagulated patients.¹

Dalhousie University Clinical Frailty Scale is a simplified scale to assess frailty.⁴

Mobility score is a simple noting of patient mobility at each visit- ambulating without assist, ambulating with cane, ambulating with walker, or arrived in wheelchair.

Time in Therapeutic Range (TTR) will be calculated utilizing the Rosendaal method of percentage days in therapeutic range in the past 6 months.

6 Analysis Plan

Compare by decade:

Sex

Living arrangement

Alcohol use

CHA2DS2-VASc score

HAS-BLED score

Dalhousie University Clinical Frailty Scale

Mobility score

TTR for 2 years and best and worse 6 months

Death secondary to anticoagulation

Death secondary to cardiovascular causes

Number of hospitalizations

Major bleeding defined as any bleeding meeting at least one of the following criteria:

- Fatal bleeding
- Symptomatic bleeding in a critical area or organ, such as intracranial, intraspinal, intraocular, retroperitoneal, intraarticular or pericardial or intramuscular with compartment syndrome, and/or
- Bleeding causing a fall in hemoglobin level of 2 g/dl or more, or leading to transfusion of two or more units of whole blood or red cells.²

CNS Bleeds with death, disability, or no disability

Embolic ischemic stroke

Non embolic ischemic stroke

Mechanism unknown ischemic stroke

Hemorrhagic stroke non traumatic

Traumatic intracerebral hemorrhage

Traumatic subdural hemorrhage

Cardiovascular events (non stroke type)

7 Confidentiality

Subject information will be kept in the PBMC Clinical Research office which is locked when unattended. Information entered into a database will be housed on a PBMC shared drive which is password protected. Information about study subjects will be kept confidential and managed according to the requirements of the Health Insurance Portability and Accountability Act of 1996 (HIPAA).

- Protected health information (PHI) which will be collected from subjects in this study include, demographics, medical history, medication list, information related to adverse events, symptoms related to atrial fibrillation and the use of anticoagulants.
- The investigator and his designees will have access to this information.

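### Chi-squared, with no small-count rule, is the only categorical test named; for the protocol's narrow stroke and CNS-bleed types its P values can be unreliable

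*SAP*

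**What the plan says.** The SAP is one paragraph. It compares three age groups ("we attempted to detect differences in outcomes among age groups (70-79, 80-89, and 90" and over) and names its methods in one sentence: "Student t tests and chi-squared tests were conducted to compare data between groups". The threshold is "Statistical significance was set at $P < .05$ with a 95% confidence interval". It does not say whether the chi-squared test is run across all three groups or pairwise, or whether a continuity correction is used. It has no small-count rule and no interval method. Its secondary outcomes are broad: death from any cause, stroke and major bleeding.

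The protocol goes further. Section 6 lists outcomes to be compared by decade. They include ischemic stroke split by mechanism, non-traumatic hemorrhagic stroke, "Traumatic intracerebral hemorrhage", traumatic subdural hemorrhage, and "CNS Bleeds with death, disability, or no disability". That section names no test.

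Group size is set by recruitment. Under section 4.3, "All patients aged 90 years or older who fit the criteria will be approached about participation in the study", and the two younger decades are matched to that number (for example, "An equal number of patients from the ACS who are aged 80-89 years"). The introduction says "Almost 15% of patients with atrial fibrillation followed by the Pen Bay Anticoagulation Service are over 90 years old", but the clinic total is not given, so the number per decade cannot be derived.

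**The concern.** Chi-squared is the only categorical test named in either document. Either it is applied to the narrow event types in protocol section 6, or those comparisons have no stated method. In both cases the SAP needs text.

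The chi-squared P value relies on a large-sample approximation that fails when only a handful of events are spread over three groups. A few events falling in one decade could be declared an age effect, and a type with one or two events could show nothing whatever the truth. Evaluating safety in the very old is a stated objective of the protocol (section 2), so a P value of either kind could carry weight that the data do not support.

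**Working it through.** **Inputs.** From the documents: three groups, equal numbers intended, threshold 0.05. Assumed, because the documents give no figures: 30, 50 or 100 patients per decade and 24-month risks of 1-2% for a narrow event type. The test is taken as the uncorrected Pearson test on a 3×2 table (2 df, critical value 5.991). The plan states no size, power or event count, so there is no figure to reproduce.

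**Three events, all in one decade.** With n per group, the expected count is 1 per group and the pooled risk is 1/n.

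- Chi-squared = (2² + 1² + 1²) / (1 − 1/n) = 6n/(n − 1). This exceeds 6, and so 5.991, for every n.
- With 2 df, P = exp(−3n/(n − 1)).
- Exact P = 3·C(n,3)/C(3n,3) = (n − 1)(n − 2) / [(3n − 1)(3n − 2)].

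| n per decade | Chi-squared | Chi-squared P | Exact P |
|---|---|---|---|
| 30 | 6.21 | 0.045 | 812/7832 = 0.104 |
| 50 | 6.12 | 0.047 | 2352/22052 = 0.107 |
| 100 | 6.06 | 0.048 | 9702/89102 = 0.109 |

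**One or two events in total.** The largest possible statistic is 2/(1 − 1/(3n)) for one event and 4/(1 − 2/(3n)) for two. At n = 50 these are 2.01 (P = 0.365) and 4.05 (P = 0.132), so rejection is impossible. An exact test cannot reject here either: with both events in one decade its P is (n − 1)/(3n − 1) = 49/149 = 0.33. This is a lack of information, not a fault that another test repairs.

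**Size given the number of events** (n = 50, exact enumeration): 0% for one or two events, 10.7% for three, 3.4% for four, 1.1% for five, 4.8% for six. The nominal 5% is missed in both directions.

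**Size averaged over the number of events** (exact enumeration):

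| n per decade | Chi-squared, risk 1% / 2% | Fisher-Freeman-Halton, risk 1% / 2% |
|---|---|---|
| 30 | 0.5% / 2.0% | 0.04% / 0.29% |
| 50 | 1.5% / 3.4% | 0.19% / 1.00% |
| 100 | 3.5% / 4.0% | 0.82% / 1.98% |

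The mid-P version at n = 50 gives 0.20% / 1.13%, also below chi-squared.

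**Power.** For true risks of 2/4/8% by decade and n = 50, power is 19.7% for chi-squared and 16.7% for the exact test.

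**Zero events.** The exact two-sided 95% upper limit for 0/n is 1 − 0.025^(1/n): 11.6% at n = 30, 7.1% at n = 50, 3.6% at n = 100. At a true risk of 2%, the chance of 0/50 is 0.98^50 = 36%.

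**Sensitivity to the unstated choices.** In an uncorrected pairwise test with equal groups, a k-to-0 split gives k/(1 − k/(2n)). At n = 50, three events give P = 0.079. Four give 4/0.96 = 4.17, P = 0.041, against an exact P of 2·C(50,4)/C(100,4) = 0.117. The same problem therefore appears one event later. A continuity correction would remove it. With unequal groups the thresholds move: at 60/50/30, two events both in the smallest group give chi-squared 7.44, P = 0.024, with exact P = 435/9730 = 0.045.

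**The case against.** The case against has four parts.

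- **Conservatism.** A reader might infer that the test fails because its size is far below 5%. That reading is not supported. Size below 5% still controls type I error on average; the low figures depend on assumed group sizes and risks; and at 100 per decade with risks of 1-2% the size is 3.5-4.0%. Exact and mid-P tests are lower still in these settings, so conservatism cannot be the reason to switch. This objection stands in full.
- **Link to the subtypes.** The SAP does not itself apply chi-squared to the narrow types, and its own secondary outcomes are already broad. This stands: the link runs through protocol section 6, which asks for the comparison and names no test. It narrows the point but leaves the gap open.
- **False reassurance.** A reader might also infer that the plan will treat a non-significant result as showing no difference by age. Neither document says so. The SAP speaks only of attempting to detect differences, and the protocol's introduction already suggests higher thrombotic and hemorrhagic risk in the very old. It is a possible misreading to guard against, not a statement in the plan.
- **Intervals.** The SAP names no interval method, so a normal-approximation interval that shrinks to 0-0 when no events occur is a possibility only.

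The primary outcome, time in therapeutic range, is not affected. Low power with few events belongs to the design, and no choice of test cures it.

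**Conclusion.** The concern holds in a limited form. The SAP has no method for sparse tables, while the protocol compares outcomes that may well be sparse. For three equal groups compared by the uncorrected test, the three-event result needs no assumed risk: chi-squared gives P < .05 at any group size, while the exact P is about 0.10 to 0.11 at 30 to 100 per decade. With one or two events the test cannot reject. The averaged sizes and the power figures rest on assumed group sizes and risks. The result depends on near-equal groups and on how the test is run, which the SAP leaves open. The consequence is confined to the narrow stroke and CNS-bleed types and to any broad secondary outcome that turns out to have few events.

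**What to change.** In the SAP:

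1. Test only the broad outcomes (all-cause mortality, stroke, major bleeding) and report the stroke and CNS-bleed subtypes as counts and percentages by decade, without P values.
2. State that the comparison is across the three decades. Where any expected count is below 5, use the Fisher-Freeman-Halton exact test, so that a 3-0-0 split is not called significant.
3. Report events and risk in each decade with exact (Clopper-Pearson) 95% intervals, and intervals for the differences between decades. Base the safety statement on these intervals.
4. State that a non-significant result is not evidence of no difference by age.

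The cost is a few sentences in the SAP and a few lines of code. The subtypes are no longer tested, and the exact test gives up about 3 percentage points of power in the 2/4/8% example at 50 per decade.
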